7.1.1. Daprodustat Dosing Information

Doses of daprodustat to be administered are based on the rhEPO dose at randomization (Day 1) as described in [Table 2](#).

Table 2 Daprodustat Doses

Darbepoetin alfa ($\mu\text{g}/4$ wk SC/IV)	Epoetin alfa (convert SC to IV U/week) ¹	Daprodustat dose (mg, once daily)
20 to 30	1500 to 2000	1
>30 to 300	>2000 to <20000	2
>300	≥ 20000	4

¹ Standardized rhEPO IV dose (U/week) = $161/113 \times (\text{epoetin SC dose (units)/frequency})$

7.1.2. rhEPO Dosing Information

Participants are required to be currently treated with stable doses ($\leq 50\%$ change in 4-weekly dose) of rhEPO for at least 8 weeks prior to and including the screening period. The dose of rhEPO to be administered during the study as randomized study treatment will be the rhEPO dose at randomization (Day 1). This dose is to be administered whether a participant is randomized to rhEPO on Treatment Period 1, or is switching back to rhEPO following 4 weeks of administration of daprodustat on Treatment Period 2.

7.1.3. ⁵⁷Fe Dosing Information

An oral solution will be administered containing 10 mg of ⁵⁷Fe as ferrous sulfate. Exact doses will be measured, calculated, and captured for each individual participant. The solution is to be taken following an overnight fast. Further details will be outlined in the compounding document and SRM.

7.1.4. ⁵⁸Fe Dosing Information

An oral solution will be administered containing 3 mg of ⁵⁸Fe as ferrous sulfate with 7 mg of ⁵⁶Fe as ferrous sulfate (natural abundance Fe). Exact doses will be measured, calculated, and captured for each individual participant. The solutions are to be taken following an overnight fast. Further details will be outlined in the compounding document and SRM.

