
Study intervention
	
 • Daprodustat dosing information: 
  
 Darbepoetin alfa ($\mu\text{g}/4 \text{ wk SC/IV}$)	Epoetin alfa (convert SC to IV U/week)¹	Daprodustat dose (mg, once daily)	
   
 20 to 30	1500 to 2000	1	
 
 >30 to 300	>2000 to <20000	2	
 
 >300	≥ 20000	4	
  
 
¹ Standardized rhEPO IV dose (U/week) = $161/113 \times (\text{epoetin SC dose (units)/frequency})$
 
 • rhEPO Dosing Information 
 ➤ Participants are treated with stable doses ($\leq 50\%$ change in 4-weekly dose) of rhEPO for at least 8 weeks prior to and including the screening period. 	Darbepoetin alfa ($\mu\text{g}/4 \text{ wk SC/IV}$)	Epoetin alfa (convert SC to IV U/week) ¹	Daprodustat dose (mg, once daily)	20 to 30	1500 to 2000	1	>30 to 300	>2000 to <20000	2	>300	≥ 20000	4
Darbepoetin alfa ($\mu\text{g}/4 \text{ wk SC/IV}$)	Epoetin alfa (convert SC to IV U/week) ¹	Daprodustat dose (mg, once daily)											
20 to 30	1500 to 2000	1											
>30 to 300	>2000 to <20000	2											
>300	≥ 20000	4											

Overview of Study Design and Key Features																
	
 • 57Fe Dosing Information 
 ➤ A 57Fe ferrous sulfate oral solution (10 mL) will be administered containing 10 mg of 57Fe (iron concentration at 1 mg/mL with 1:1 molar ratio ascorbic acid in the solution). • 58Fe Dosing Information A 58Fe ferrous sulfate oral solution (3 mL) will be administered containing 3 mg of 58Fe followed by a 56Fe (natural abundance) ferrous sulfate oral solution (7 mL) containing 7 mg of 56Fe. Both solution contains iron at 1 mg/mL with ascorbic acid at 1:1 molar ratio. 															

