4.2.1. Definition of endpoint(s)

Objectives	Endpoints
Primary Objectives	Primary Endpoints

 Compare the efficacy of daprodustat to rhEPO (i.e., epoetin alfa or darbepoetin alfa) on iron absorption 	
 Difference in fractional oral iron absorption (%) between daprodustat and rhEPO

The process for calculating the fractional iron absorption will depend on the sequence and is defined separately for each iron isotope. Formulas will be based on IAEA guidance for assessment of iron bioavailability in humans (IAEA 2012).

Sequences A and C:

S. No.	Parameters	Period 1 - ⁵⁷ Fe Fractional Oral Iron Absorption	Period 2 - ⁵⁸ Fe Fractional Oral Iron Absorption	Details
Parameters provided in data				
1	Hgb in g/dL	Hgb Day 15	Hgb Day 43	We will use the Hgb (g/dL) measurement from the day of isotope dosing (Day 15 for Period 1, Day 43 for Period 2)
2	BV in mL	70 * Day 15 Weight	70 * Day 43 Weight	We will assume a blood volume (BV) of 70 mL/kg and a fixed volume per kg. Weight represents the

S. No.	Parameters	Period 1 - ⁵⁷ Fe Fractional Oral Iron Absorption	Period 2 - ⁵⁸ Fe Fractional Oral Iron Absorption	Details
				weight measurement (kg) taken on the day of dosing (Day 15 for Period 1, Day 43 for Period 2).
3a	Baseline ⁵⁷ Fe/ ⁵⁶ Fe	0.02317	N/A	Natural abundance measure for iron isotope, which is an assumed constant for this analysis.
3b	Baseline ⁵⁸ Fe/ ⁵⁶ Fe	N/A	Value3b	Baseline measurement for ⁵⁸ Fe in

S. No.	Parameters	Period 1 - ⁵⁷ Fe Fractional Oral Iron Absorption	Period 2 - ⁵⁸ Fe Fractional Oral Iron Absorption	Details
				
Period 2 will utilize the Day 43 blood sampling for isotopic iron, as the ⁵⁷Fe solution in Period 1 may contain small quantities of ⁵⁸Fe. This measurement will be provided by Cornell University.

4a	Enriched ⁵⁷ Fe/ ⁵⁶ Fe	Value4a	N/A	Enriched iron value is calculated internally on the

S. No.	Parameters	Period 1 - ⁵⁷ Fe Fractional Oral Iron Absorption	Period 2 - ⁵⁸ Fe Fractional Oral Iron Absorption	Details
				spectroscopy instrument and provided by Cornell University.
4b	Enriched ⁵⁸ Fe/ ⁵⁶ Fe	N/A	Value4b	Enriched iron value is calculated internally on the spectroscopy instrument and provided by Cornell University.
Parameters derived by S&P				
5	% excess	$\frac{\text{Value4a} - \text{Value3a}}{\text{Value3a}} * 100$	$\frac{\text{Value4b} - \text{Value3b}}{\text{Value3b}} * 100$	S&P will derive this value. Δ% excess is used

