7	Total incorporated iron isotope (mg)	$Total\ incorporated\ ^{58}Fe = Parameter5 * Parameter6 * 0.0214 * 0.50797$	$Total\ incorporated\ ^{57}Fe = Parameter5 * Parameter6 * 0.0214 * 0.49203$	S&P will derive this value. We assume

S. No.	Parameters	Period 1 - ⁵⁸ Fe Fractional Oral Iron Absorption	Period 2 - ⁵⁷ Fe Fractional Oral Iron Absorption	Details
				the fractional abundance of ⁵⁷ Fe in mg is (0.0214 g * 0.01), and the fractional abundance of ⁵⁸ Fe in mg is (0.00287 g * 0.01).
8	% iron isotope incorporated	$\% \text{ } ^{58}\text{Fe Incorporated} = \frac{\text{Parameter7}}{58\text{Fe Dose}}$	$\% \text{ } ^{57}\text{Fe Incorporated} = \frac{\text{Parameter7}}{57\text{Fe Dose}}$	S&P will derive percent of iron isotope incorporated. ⁵⁷ Fe and ⁵⁸ Fe doses (mg) will be determined using the

S. No.	Parameters	Period 1 - ⁵⁸ Fe Fractional Oral Iron Absorption	Period 2 - ⁵⁷ Fe Fractional Oral Iron Absorption	Details
				density of ferrous sulfate (FeSO ₄) oral solution (1g/mL), the dose of oral solution (in mL), and concentration of elemental iron (1mg/mL).
9	Assumed % iron isotope absorbed if 80%	$\% \text{ } ^{58}\text{Fe absorbed} = \text{Parameter8} * \frac{100}{80}$	$\% \text{ } ^{57}\text{Fe absorbed} = \text{Parameter8} * \frac{100}{80}$	S&P will derive this value, using the formula suggested by the IAEA for the assessment

S. N o.	Para meter s	Period 1 - ⁵⁸ Fe Fractional Oral Iron Absorption	Period 2 - ⁵⁷ Fe Fractional Oral Iron Absorption	Detail s
				of iron bioavailability (IAEA pg.38). Parameter 9 defines the fractional oral iron absorption endpoint, assuming 80% of the absorbed Fe is incorporated into RBCs.

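### SAP Parameter 8 divides by total iron rather than isotope: the dose has no enrichment term, although the SAP allows that the label solutions may be impure

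*SAP*

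**What the plan says.** In both sequence tables of SAP 4.2.1, Parameter 8 divides the incorporated isotope (mg) by the ⁵⁷Fe or ⁵⁸Fe dose. That dose is to come from a density of 1 g/mL, "the dose of oral solution (in mL), and concentration of elemental iron (1mg/mL". Neither table has a factor for the share of that iron that is the labelled isotope.

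For Sequences A and C, Parameter 3b takes the Period 2 baseline from the Day 43 sample, "as the ⁵⁷Fe solution in Period 1 may contain small quantities of ⁵⁸Fe". Parameter 3a for Sequences B and D gives the mirror-image reason.

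The stated amounts are:
- SAP 1.2, ⁵⁷Fe: "57Fe ferrous sulfate oral solution (10 mL) will be administered containing 10 mg of 57Fe", at 1 mg of iron per mL.
- SAP 1.2, ⁵⁸Fe: "58Fe ferrous sulfate oral solution (3 mL) will be administered containing 3 mg of 58Fe", then a separate 7 mL natural-abundance solution with 7 mg of iron. Both are at 1 mg of iron per mL.
- Protocol 7.1.4: "An oral solution will be administered containing 3 mg of ⁵⁸Fe as ferrous sulfate with 7 mg of ⁵⁶Fe".
- Protocol 7.1.3 and 7.1.4, on recording: "Exact doses will be measured, calculated, and captured for each individual participant".

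**The concern.** Volume times elemental-iron concentration gives iron, not isotope. The two agree only for a pure tracer at exactly the nominal strength. The SAP itself doubts the purity when it sets the Period 2 baseline, then ignores purity when it computes the dose.

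The dose divides every primary-endpoint value, so a proportional error in it passes straight into each absorption percentage and into the treatment difference. The isotope term in the model of SAP 4.2.2 removes an additive shift between isotopes. It does not restore a multiplicative scale. Absolute scale matters here: Protocol 5.4 values fractional absorption partly because it can be compared with results in people without anaemia.

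The concentration is also fixed at 1 mg/mL, although Protocol 7.1 has the solutions compounded extemporaneously and the protocol promises individually measured doses.

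**Working it through.** **Inputs.** Volumes of 10 mL (⁵⁷Fe label), 3 mL (⁵⁸Fe label) and 7 mL (carrier), each at 1 mg/mL: SAP 1.2. Natural abundance of ⁵⁸Fe, 0.00287: the value that the note to Parameter 7 assigns to ⁵⁸Fe. Difference of 11 points and SD of 10.7: SAP 5. Fasted absorption of 14.71%: Protocol 5.4. Enrichment e is not in the documents; 0.90 to 1.00 is assumed, the same for both isotopes. The Parameter 7 numerator is taken as given.

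**1. The plan's own figures.** 10 mL × 1 mg/mL = 10 mg and 3 mL × 1 mg/mL = 3 mg. Both match SAP 1.2, a ratio of 1.00 for each isotope.

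**2. Dose with enrichment.** The ⁵⁷Fe dose is 10e. The carrier holds 7 × 0.00287 = 0.020 mg of natural ⁵⁸Fe, so all the ⁵⁸Fe given is 3e + 0.020. Reported over true absorption is the correct dose divided by the SAP dose.

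**3. Effect on the treatment difference.** Let f57 and f58 be those ratios, μ the rhEPO mean and D the true difference. Daprodustat minus rhEPO is then
- Sequences A and D: f58(μ + D) − f57·μ
- Sequences B and C: f57(μ + D) − f58·μ

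Over the four balanced sequences μ cancels and the mean is D(f57 + f58)/2.

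| e (assumed) | ⁵⁷Fe dose, mg | f57 | ⁵⁸Fe dose, mg | f58 | True 11 points reads |
|---|---|---|---|---|---|
| 0.90 | 9.0 | 0.900 | 2.720 | 0.907 | 9.94 |
| 0.95 | 9.5 | 0.950 | 2.870 | 0.957 | 10.49 |
| 0.99 | 9.9 | 0.990 | 2.990 | 0.997 | 10.93 |
| 1.00 | 10.0 | 1.000 | 3.020 | 1.007 | 11.04 |

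Without the carrier's ⁵⁸Fe, the first three rows read 9.90, 10.45 and 10.89. A least-squares fit of treatment, period, isotope and participant on the balanced design gives the same three values.

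**4. Level.** A ⁵⁷Fe value reported as 14.71% would be 14.71/0.90 = 16.34% at e = 0.90 and 14.71/0.99 = 14.86% at e = 0.99.

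**5. Direction for ⁵⁸Fe.** The SAP's 3 mg equals 3e + 0.020 at e = (3 − 0.02009)/3 = 0.9933. Above that, counting the carrier, the SAP denominator is slightly too small (0.7% at e = 1).

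**6. Effect on the test.** A common factor scales estimate and SD alike. At 0.90, 9.9/9.63 = 1.028, the same as 11/10.7. The two-sided paired t-test power (n = 12, 11 df) is 89.9%, against the plan's 90%, and a common factor leaves it unchanged.

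**The case against.** The strongest reply is that the documents equate milligrams of iron with milligrams of isotope in each label solution, so the rule returns the stated doses exactly. That stands. A reader might infer that the denominator is too large as a matter of fact. The documents do not show this: they give no enrichment, they only allow that impurity may exist, and for ⁵⁸Fe the direction can reverse.

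A reader might also infer that the ⁵⁸Fe dose will be taken as 10 mL × 1 mg/mL = 10 mg. That would make ⁵⁸Fe values 3.3-fold too low and turn a true 11 points into 11 × (1 + 0.3)/2 = 7.15. The documents do not support that reading. SAP 1.2 gives separate 3 mL and 7 mL solutions with 3 mg of ⁵⁸Fe in the first, and Protocol 7.1.4 goes on to speak of solutions in the plural. What remains is that Parameter 8 does not name the volume and that Protocol 7.1 lists a single combined product.

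It is also fair to say that the volume given is an input rather than a constant, that no passage reports batch-to-batch error, and that the specification document, the compounding document and the reference manual are unseen. An enrichment factor could sit there, but the SAP formula as written has no place for one. Finally, the endpoint already rests on fixed scale assumptions (70 mL/kg blood volume, 80% incorporation). Unlike those, isotope fraction is a property of the material that can be looked up.

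**Conclusion.** The point holds as an inconsistency in the definition of the primary endpoint. Parameter 8 computes total iron and has no enrichment term, while the baseline rule in the same section provides for impurity. Its numerical effect is conditional. At an assumed enrichment of 90–99%, values and the treatment difference are understated by about 1–10% relative, with a true 11 points reading about 9.9–10.9. At full enrichment and exactly 1 mg/mL the ⁵⁷Fe error is zero, and the ⁵⁸Fe error is at most 0.7% in the other direction.

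A purity factor common to both isotopes barely touches the test. Isotope is balanced across treatments, so neither arm is favoured. What suffers is the scale of the reported absorption, difference and confidence interval. Concentration error by batch cannot be sized from the documents.

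This should be fixed as a cheap improvement. It is not a flaw that threatens the trial's conclusion.

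**What to change.** In Parameter 8 of both tables, define dose (mg of isotope) = the participant's measured amount of label solution × the batch iron concentration × the certified mass fraction of that isotope. Use the individually captured doses that the protocol promises.

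Add the carrier's natural ⁵⁸Fe (about 0.020 mg) to the ⁵⁸Fe dose, or record why it is left out. There is an argument for leaving it out, since Parameter 5 counts only enrichment above baseline, which natural-abundance iron hardly moves. Either way, state the choice.

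As a minor clarification, say that the volume entered for ⁵⁸Fe is that of the label solution (3 mL in SAP 1.2), not the 10 mL total. Reconcile the product descriptions in Protocol 7.1, Protocol 7.1.4 and SAP 1.2.

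The cost is SAP wording and retrieval of the batch assays and isotope certificates. No new samples or participants are needed.

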4.2.2. Main analytical approach

Endpoint / Variables

 Fractional oral iron absorption (%)
Model Specification

 To compare daprodustat to rhEPO on fractional iron absorption, a mixed effects model will be fitted Terms fitted in the mixed effect model will include:

Endpoint / Variables

 • Fixed effect: treatment, period, and iron isotope • Random effect: participant • The Kenward and Roger method for approximating the denominator degrees of freedom and correcting for bias in the estimated variance-covariance of the fixed effects will be used. • Using PROC MIXED in SAS, the covariance for the random participant effect (G matrix) will be fit using an unstructured covariance structure by specifying ‘type=UN’ on the RANDOM line. 
 • In the event that this model fails to converge, alternative covariance structures may be considered such as Variance Components or Compound Symmetry. • Akaike’s Information Criteria (AIC) will be used to assist with the selection of covariance structure.
Model Checking & Diagnostics

 • For the Mixed Model, model assumptions will be checked, and appropriate adjustments may be applied based on the data. • Distributional assumptions underlying the model used for analysis will be examined by obtaining a normal probability plot of the residuals and a plot of the residuals versus the fitted values (i.e. checking the normality assumption and constant variance assumption of the model respectively) to gain confidence that the model assumptions are reasonable. • If there are any departures from the distributional assumptions, alternative transformations, such as data squared or square root of data, will be explored. • Non-parametric analyses will be conducted if the normality assumption does not hold.
Model Results Presentation

Fractional oral iron absorption will be summarized using n, mean, SD, median, minimum, and maximum.
 
Point estimates, corresponding 95% confidence intervals, and two-sided p-values will be constructed for the comparison of efficacy of daprodustat to rhEPO.

4.2.3. Sensitivity analyses

A sensitivity analysis for the primary analysis will be performed using the same mixed modelling approach, except with the mITT population.

4.3. Secondary Endpoint(s) Analyses

Markers of iron status endpoints will include serum iron, transferrin, transferrin saturation, soluble transferrin receptor, ferritin, hepcidin, and erythroferrone.

Indices of erythropoiesis endpoints will include Hgb, haematocrit, red blood cell number, mean corpuscular volume, reticulocyte Hgb, and reticulocyte number.

Change from baseline (n, mean, standard deviation, 95% CI of mean, median, minimum, and maximum) at Day 14, Day 29, Day 43, and Day 57 will be calculated for iron markers and indices of erythropoiesis by treatment group. Day 1 (Pre-dose) and Day 29 (Pre-dose) will be the baseline for both iron markers as well as indices of erythropoiesis for their respective periods.

Descriptive statistics (n, arithmetic mean, standard deviation, 95% CI, minimum, median, and maximum) will be calculated for iron markers and indices of erythropoiesis at each scheduled visit by treatment group. No formal statistical testing will be performed. Hepcidin and ferritin values will be log-transformed prior to summary.

All analyses on secondary endpoints will be based on the “Evaluable” population, unless otherwise specified.

4.4. Safety Analyses

The safety analyses will be based on the “Safety” population, unless otherwise specified.

4.4.1. Extent of Exposure

- Number of days of exposure to study drug will be calculated based on the formula:
Duration of Exposure in Days = Treatment Stop Date – (Treatment Start Date) + 1
- Duration will be summarized by treatment group. Each subject will contribute duration of exposure to the treatment taken.
- Participants who were randomized but did not report a treatment start date will be categorised as having zero days of exposure.

A listing and summary table of exposure will be created.

4.4.2. Adverse Events

Adverse events analyses including the analysis of adverse events (AEs), Serious AEs (SAEs) and other significant AEs will be based on GSK Core Data Standards. An overview summary of AEs, including counts and percentages of participants with any AE, AEs related to study intervention, SAEs related to study intervention, fatal SAEs, and fatal SAEs related to study intervention will be produced. Adverse events will be coded using the standard Medical Dictionary for Regulatory Affairs (MedDRA dictionary). A summary of number and percentage of participants with any adverse events by maximum severity will be produced. A separate summary will be provided for

study intervention-related AEs. A study intervention-related AE is defined as an AE for which the investigator classifies the possible relationship to study intervention as “Yes”. A worst-case scenario approach will be taken to handle missing relatedness data, i.e. the summary table will include events with the relationship to study intervention as ‘Yes’ or missing. The summary table will be displayed by PT only. All SAEs will be tabulated based on the number and percentage of participants who experienced the event. Separate summaries will also be provided for study intervention-related SAEs. The summary tables will be displayed by PT and SOC. A study intervention-related SAE is defined as an SAE for which the investigator classifies the relationship to study intervention as “Yes”. A worst-case scenario approach will be taken to handle missing data, i.e. the summary table will include events with the relationship to study intervention as ‘Yes’ or missing. Summaries and listings of adverse events will include treatment sequence. A listing of AEs that occur during Follow-up will be provided. AEs leading to permanent discontinuation of study intervention and study intervention related AEs leading to permanent discontinuation of study intervention will be listed.

4.4.2.1. Adverse Events of Special Interest

Adverse Events of Special Interest (AESI) have been identified based on non-clinical studies with daprodustat, clinical experience with rhEPOs, and current information regarding HIF-regulated pathways in mediating hypoxia-associated pathophysiology. The following will be considered adverse events of special interest for the purpose of analyses:

- Thrombosis and/or tissue ischemia secondary to excessive erythropoiesis
- Death, MI, stroke, heart failure, venous thromboembolism, thrombosis of vascular access
- Cardiomyopathy
- Pulmonary artery hypertension
- Cancer-related mortality and tumor progression and recurrence
- Esophageal and gastric erosions
- Proliferative retinopathy, macular edema, choroidal neovascularization
- Exacerbation of rheumatoid arthritis
- Worsening of hypertension

The summary of event characteristics will be provided for each AESI respectively, including number of participants with any event, number of events, number of participants with any event that is serious. The percentage will be calculated in two ways, one with number of participants with event as the denominator and the other with total number of participants as the denominator. The worst-case approach will be applied at participant level for the maximum grade, i.e. a participant will only be counted once as the worst case from all the events experienced by the participant. For action taken to an event, a participant will be counted once under each action, e.g. if a participant has an event leading to both study intervention discontinuation and dose reduction, the participants will be counted once under both actions.

4.4.2.2. COVID-19 Assessment and COVID-19 AEs

A standardized MedDRA Query (SMQ) will be used to identify all COVID-19 AEs. COVID-19 assessments for participants with COVID-19 AEs will be summarized.

4.4.3. Additional Safety Assessments

4.4.3.1. Possible Suicidality Related Adverse Events

A listing of possible suicidality related- adverse events (PSRAE) will be produced based on GSK Core Data Standards. The listing will be sorted by site id, unique subject id, then chronologically within subject.

4.4.3.2. Laboratory Data

Laboratory evaluations including the analyses of Chemistry laboratory tests, Hematology laboratory tests, Urinalysis, and liver function tests will be based on GSK Core Data Standards. When collected throughout the treatment period, laboratory data will be summarized based on observed values by visit and treatment sequence, as well as change from baseline by visit and treatment sequence. For laboratory data collected only at screening and follow-up visits, no summary will be produced. A listing of all laboratory data and a listing of PCI laboratory data will be produced.

Laboratory data includes the following variables:

Assessments	Parameters		
Haematology	
 • Platelet Count • Hematocrit • Hgb 	RBC Indices: 
 • MCV • MCH • %Reticulocytes 	WBC count with Differential: 
 • Neutrophils • Lymphocytes • Monocytes • Eosinophils • Basophils
Clinical Chemistry	
 • BUN • Creatinine • Glucose • Potassium • Sodium • Calcium 	
 • Aspartate Aminotransferase (AST)/Serum Glutamic-Oxaloacetic Transaminase (SGOT) 	
 • Total and direct bilirubin
	
 • Alanine Aminotransferase (ALT)/ Serum Glutamic-Pyruvic Transaminase (SGPT) 	
 • Alkaline phosphatase 	
 • Total Protein

Assessments	Parameters
Routine Urinalysis	
 • Specific gravity • pH, glucose, protein, blood, ketones, bilirubin, urobilinogen, nitrite, leukocyte esterase by dipstick • Microscopic examination (if blood or protein is abnormal)
Other Laboratory Analyses	
 • Follicle-stimulating hormone and estradiol (as needed in women of non-childbearing potential only) • Urine human chorionic gonadotropin (hCG) pregnancy test (as needed for women of childbearing potential) • HIV antibody • Folate, high sensitivity C-reactive protein, Vitamin B12

Separate summary tables for haematology, and chemistry laboratory tests will be produced. Liver function laboratory tests will be included with chemistry lab tests. Summaries of other laboratory analyses collected only at screening will not be produced.

Summaries of hepatobiliary laboratory events including possible Hy’s law cases will be provided in addition to what has been described above. Possible Hy’s law cases are defined as any elevated alanine aminotransferase (ALT) $>3\times$ upper limit of normal (ULN), total bilirubin $\geq 2\times$ ULN and alkaline phosphatase (ALP) $<3\times$ ULN/missing. Total bilirubin $\geq 2\times$ ULN can be within 28 days following the ALT elevation and if direct bilirubin is available on the same day, it must be $\geq 35\%$ of total bilirubin. ALP $<3\times$ ULN/missing means it is satisfied unless the ALP is $\geq 3x$ ULN at the time of bilirubin elevation. The summary will be produced for worst case post baseline only.

